#### **13.3.3. Efficacy Analysis**

##### **13.3.3.1. Relapse-free survival**

Relapse-free survival will be censored on the date of the last evaluable CT scan on trial for subjects who do not have recurrence and who do not die while on trial. Subjects without any post baseline CT scans will have their RFS time censored on the date of randomization. Subjects who withdraw from the trial (including withdrawal of consent and lost to follow-up) will be censored at the last of the last CT scan. For disease recurrence documented by CT between scheduled evaluations, the actual date of the scan will be used. For death or recurrence after no more than

1 missed evaluation, the date of the event will be the date of recurrence or death, whichever occurs first. For death or recurrence after more than 1 missed evaluation, RFS will be censored at the last evaluable disease assessment.

RFS (in months) is calculated as:

- $[(\text{date of recurrence/death} - \text{date of randomization}) + 1]/30.4375$

### **13.3.3.2. Analysis of Biomarker Response**

Response will be defined as any subject with a reduction or clearance of biomarker (ctDNA or serum tumor biomarker) compared with baseline [[Tie et al, 2019](#)]. Subjects who do not attain a response for any reason (eg, missing data due to withdrawal) will be counted as non-responders. The subset of subjects with biomarker clearance will also be summarized.

### **13.3.3.3. Analysis of Duration of Biomarker Response**

Duration of biomarker response (ie, reduction or clearance) will be reported for subjects who meet the biomarker reduction or clearance definitions.

- Duration of biomarker reduction is calculated from the date of the first biomarker blood test with a reduction compared to baseline, until the earliest date of any of the following events: (1) subsequent increase in biomarker; (2) subsequent disease recurrence; or (3) death due to any cause.
- Duration of biomarker clearance is calculated from the date of the first negative ctDNA test or the date when the serum tumor biomarker is  $\leq$ ULN to the earliest date of any of the following events: (1) subsequent positive ctDNA test or subsequent serum tumor biomarker  $>$ ULN; (2) subsequent disease recurrence; or (3) death due to any cause.

If a subject has not experienced any of the events for reduction or clearance, duration of response will be censored on the date of the last biomarker assessment.

Response duration will be summarized for each cohort. Assessment of biomarker response duration is considered supportive of the primary biomarker response analysis and is not considered part of the fixed sequence testing procedure to control overall type 1 error.

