## 6. INVESTIGATIONAL PLAN

### 6.1. Overall Trial Design

ELI-002-001 is an open-label, Phase 1 trial of ELI-002 immunotherapy as adjuvant treatment for subjects with KRAS/NRAS mutated PDAC and other solid tumors who are at high risk for relapse (ie, presence of isolated tumor cells as detected by ctDNA or elevated serum tumor biomarkers in the subject's body, in which the primary tumor has been removed and is currently without clinical signs of disease). High relapse risk is defined by either a ctDNA-positive result or an elevated serum tumor biomarker (such as CA19-9, CEA, or CA-125).

This Phase 1 study comprises an open label, single arm, dose-escalation trial incorporating a 3+3 design in subjects with mKRAS/mNRAS solid tumors (PDAC, CRC, NSCLC, ovarian, CCA, and gallbladder carcinoma).

Approximately 18 subjects are planned to be enrolled in the study to evaluate the safety, tolerability and exploratory pharmacodynamic efficacy of SC ELI-002 using the adjuvant at 3 planned dose levels (Amph-CpG-7909 0.1 mg SC, 0.5 mg SC, 2.5 mg SC) in combination with a fixed dose of Amph-Peptides (700 µg each). Additional cohorts may be added to explore intermediate or higher dose levels. This will be based on the cumulative safety review and preliminary review of efficacy. If additional cohorts are added, this will be documented in a study memo sent to all clinical sites and submitted to IRBs, per IRB guidance.

During the study, ELI-002 will be comprised of 1.4 mg of 2 Amph modified KRAS peptides, Amph-G12D, and Amph-G12R (0.7 mg/peptide) admixed with Amph-CpG-7909 to provide ELI-002 2P. Elicio plans to investigate the use of an Amph-Peptide 7P drug product containing all 7 Amph-Peptides (G12D, G12R, G12V, G12A, G12C, G12S, G13D) admixed with Amph-CpG-7909 (ELI-002 7P) in future clinical trials.

The ELI-002-001 protocol is an open label, single arm, dose-escalation trial incorporating a 3+3 design. Subjects will receive the initial dose of ELI-002 and be monitored for  $\geq 24$  hours in order to monitor for potential AEs such as cytokine release syndrome (CRS). In addition, there will also be a 1-week stagger between enrollment of the first subject in a cohort and the subsequent subjects. In the absence of toxicity during the DLT assessment window, the ELI-002 dose will be escalated. Planned cohort dose levels are listed below:

- Cohort 1 Dose Level 1: Amph-CpG-7909 0.1 mg with Amph-Peptides
- Cohort 2 Dose Level 2: Amph-CpG-7909 0.5 mg with Amph-Peptides

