## 7. SELECTION AND WITHDRAWAL OF SUBJECTS

### 7.1. Subject Inclusion Criteria

Subjects must meet the following criteria on screening examination to be eligible to participate in the trial:

1. Male or female subjects aged  $\geq 18$  years
2. Histologically or cytologically confirmed diagnosis of solid tumor
3. Depending on the clinical site ability to access acceptable tumor sample for analysis: available tumor sample and EDTA blood sample for central lab WES biomarker analysis (preferable) or a blood sample for central lab plasma RAS ctDNA assay, which demonstrates at least 1 of the 2 mKRAS/NRAS alleles (eg, G12D or G12R) targeted by ELI-002 2P
4. High relapse risk, as evidenced by biomarker data with the last value obtained  $\geq 21$  days after surgery or last administration of adjuvant therapy, whichever comes last in the specific subject's treatment plan (values must not be attributable to a non-cancer condition, such as pancreatitis, peritonitis, postoperative leak/fistula, or biliary obstruction) as follows:
  - a. ctDNA blood test positive, or
  - b. successive rising values ( $\geq 1$  week apart) in a serum tumor biomarker (such as CA19-9, CEA, and CA-125), or
  - c. individual biomarker values CA19-9  $\geq 90$  U/mL, or CEA  $\geq 15$  ng/mL, or CA-125  $\geq 35$  U/mL
5. If subject has PDAC:
  - a. Stage I, II, III or Stage IV oligometastatic ( $< 3$  lesions in one organ) disease per current American Joint Committee on Cancer (AJCC) staging criteria, with radiographic NED (no evidence of disease) status following surgery. Equivocal radiographic findings (eg, subcentimeter lesions, potential resolving soft tissue changes after surgery) are acceptable.
  - b. Prior treatment with a standard of care chemotherapy or chemotherapy/chemoradiation (eg, FOLFIRINOX, gemcitabine/nab-paclitaxel, or 5-FU/capecitabine) according to NCCN pancreatic cancer guidelines and administered in neoadjuvant and/or adjuvant setting
  - c. Successful surgical resection (focal use of intraoperative irreversible electroporation (eg, Nanoknife®) is permitted): Complete resection (R0) or with microscopic residual disease (R1)
6. If subject has CRC:
  - a. High risk Stage II (T4N0), Stage III (T4N1-2/TanyN2), or Stage IV oligometastatic disease per current AJCC staging criteria, with radiographic NED status following surgery. Equivocal radiographic findings (eg, subcentimeter lesions, potential resolving soft tissue changes after surgery) are acceptable.

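### Protocol serum-marker clearance needs only a value at or below ULN, so a marker rising within the normal range can qualify; the SAP uses a different rule and does not record the change

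*Protocol*

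**What the plan says.** **Endpoint.** The secondary endpoint (Protocol 6.2.2) is the proportion of subjects with reduction and clearance of ctDNA. The serum marker takes its place only when ctDNA was undetectable at baseline. Protocol 13.3.3.2 says: "Response will be defined as any subject with a reduction or clearance of biomarker (ctDNA or serum tumor biomarker) compared with baseline". It adds: "The subset of subjects with biomarker clearance will also be summarized". It gives no level that defines serum clearance.

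**Clearance rule in the Protocol.** The only level is in the duration section, 13.3.3.3: "Duration of biomarker clearance is calculated from the date of the first negative ctDNA test or the date when the serum tumor biomarker is" at or below ULN. Clearance ends at a "subsequent positive ctDNA test or subsequent serum tumor biomarker" above ULN, at recurrence or at death. Durations "will be reported for subjects who meet the biomarker reduction or clearance definitions".

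**Eligibility.** Inclusion criterion 4 (Protocol 7.1) offers three alternatives: a positive ctDNA test (4a), "successive rising values" of a serum marker at least a week apart (4b), or single-value thresholds of CA19-9 90 U/mL, CEA 15 ng/mL or CA-125 35 U/mL (4c). Criterion 4b ends "week apart) in a serum tumor biomarker (such as CA19-9, CEA, and CA-125), or", so the 4c thresholds do not bind it. Section 6.1 opens differently: "High relapse risk is defined by either a ctDNA-positive result or an elevated serum tumor biomarker (such as CA19-9, CEA, or CA-125". The Synopsis agrees with that opening. Later text in 6.1 and the text under Figure 4 in 6.1.5 ask for successive rises.

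**Clearance rule in the SAP.** Table 8 defines clearance as a percent change from baseline that reaches -100%. Its duration ends at a confirmed rise above -100%. ULN does not appear. Section 14, which lists changes from the Protocol, does not mention this one.

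**The concern.** A clearance rule should identify a marker that was abnormal and became normal. The Protocol rule tests only the second half. Criterion 4b can bring in subjects for whom the first half is false, and they fall under the serum rule when their ctDNA is undetectable at baseline. Such a subject satisfies the clearance level before the first dose and still satisfies it while the marker rises, until ULN is crossed.

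Three summaries could be affected: the clearance subset, the clearance duration and, because response means reduction or clearance, the response rate of the secondary endpoint. The plan already guards against the same problem for ctDNA: section 2.2 of the SAP's immunogenicity and ctDNA addendum counts a responder only if ctDNA was detectable at baseline. Serum clearance has no matching condition.

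**Working it through.** The documents state no clearance rate or power figure, so there is none to reproduce. The check applies each written rule to the same illustrative values.

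**Inputs.** Percent change = 100 × (v − b)/b, where b is baseline and v a later value. The documents do not give the local laboratories' ULNs. Assumed ULNs, from cut-offs cited in the Protocol: CA19-9 37 U/mL (4.1.5.1), CA-125 35 U/mL (4.1.4.2), CEA 5 ng/mL (4.1.2.4). The series are invented; each baseline follows a lower screening value, so 4b is met.

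| Marker (assumed ULN) | Baseline | Later values | Percent change | Protocol: at or below ULN | SAP: -100% |
|---|---|---|---|---|---|
| CA19-9 (37) | 20 | 25, 30, 36 | +25, +50, +80 | cleared, all three | not cleared, not reduced |
| CEA (5) | 2.0 | 2.8, 3.6, 4.9 | +40, +80, +145 | cleared, all three | not cleared, not reduced |
| CA-125 (35) | 16 | 20, 28, 34 | +25, +75, +112.5 | cleared, all three | not cleared, not reduced |

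SAP Table 8 names CA19-9 and CEA but not CA-125, so its formula is applied to that row by analogy.

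**Protocol rule.** 9 of 9 rising values count as cleared. This does not depend on the assumed ULNs: any b < v ≤ ULN gives the same result, and the 20 to 30 U/mL example holds for any CA19-9 ULN of 30 or more.

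**SAP rule.** 0 of 9 count, either as clearance or as reduction. But 100 × (v − b)/b = −100 only if v = 0. A fall from 90 to 5 U/mL gives 100 × (5 − 90)/90 = −94.4%, which is not clearance although 5 is far below the assumed ULN.

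**With baseline above ULN also required.** 0 of the 9 rising values count, and the fall from 90 to 5 U/mL does count.

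**Weight of one misclassified subject, if the Protocol rule is applied.** The shift is 100/n percentage points. Limits are Clopper-Pearson, the single-group method in Protocol 13.2.1.

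| n | Shift (points) | 95% CI at 0/n | 95% CI at 1/n |
|---|---|---|---|
| 3 | 33.3 | 0 to 70.8% | 0.8 to 90.6% |
| 6 | 16.7 | 0 to 45.9% | 0.4 to 64.1% |
| 18 | 5.6 | 0 to 18.5% | 0.1 to 27.3% |

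The 18 is the three-cohort plan. SAP 8.1 lists five cohorts; at 3 to 6 subjects each that is 15 to 30 subjects, and one subject is 100/15 = 6.7 to 100/30 = 3.3 points.

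**The case against.** **The SAP does not produce this error.** This stands. A reader might infer that the final analysis will report rising, normal-range markers as cleared. It will not if Table 8 is followed: 20 to 30 U/mL is neither clearance nor reduction there. What remains is that the Protocol rule has not been openly withdrawn, and that returning to ULN without a baseline condition would bring the fault into the analysis.

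**Response is defined relative to baseline.** Section 13.3.3.2 says so, and a 50% rise is hard to read as clearance on that wording. This shows intent. But the only level a programmer can apply is the absolute one in 13.3.3.3, so the Protocol is at best ambiguous.

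**Few subjects, perhaps none, are exposed.** This also stands. A reader might infer that every 4b subject with baseline at or below ULN becomes a responder. That ignores three things: the serum marker is used only when ctDNA was undetectable at baseline; missing data count as non-response; and the first scheduled post-dose serum test is Day 148, by which time some rising markers may have passed ULN. If sites applied the elevated-marker wording of the Synopsis and 6.1, the group may be empty. The documents support no count.

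**The stakes are modest.** Clearance is a subset summary in a single-arm Phase 1 trial, and its duration is exploratory. True, but clearance is part of the only secondary endpoint, and cohorts are small.

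**Conclusion.** The fault in the Protocol text is real. Its only operational serum-clearance rule can be met by a marker that was never above ULN and is rising, and 4b can admit such a subject. The two documents also define serum clearance differently: the Protocol rule is too easy to meet for this group, the SAP rule is almost impossible to meet for anyone, and SAP section 14 does not record the difference.

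The conclusion does not extend to a bias in the final analysis as the SAP specifies it, or to any estimate of how many subjects are affected. The 17 to 33 points per cohort (5.6 at n=18) is the effect of one misclassified subject, and only if the Protocol rule is applied. The numerical examples rest on assumed ULNs; the logic does not. This should be corrected, but it does not threaten the primary objectives.

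**What to change.** - Put one serum-clearance definition in Protocol 13.3.3.2 and 13.3.3.3 and in SAP Table 8: evaluable only if baseline is above ULN; met by a post-baseline value that is at or below ULN and below baseline. Adding a baseline condition to Table 8 while keeping -100% would not be enough.
- Assess subjects with baseline at or below ULN for reduction only, and list them.
- Record the change and its reason in SAP section 14.
- Reconcile the elevated-marker wording (Synopsis and the start of 6.1) with the successive-rise wording (later in 6.1, 6.1.5 and inclusion 4b).

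The cost is a sentence or two in each document and no new data. Compared with the Protocol rule, the clearance rate may fall slightly. Compared with the SAP rule it may rise, since a fall from 90 to 5 U/mL would then count. Because the trial is open-label, the section 14 entry should be dated.

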### **13.3.3.4. Analysis of 1-Year RFS**

Exploratory analysis of 1-year RFS will be reported.

### **13.3.3.5. Analysis of OS**

Exploratory analysis of OS will be reported.

OS is calculated from the day of first ELI-002 administration to death. For subjects who are alive or lost to follow-up, OS is censored at the day the subject is last known alive as the last recorded date known alive. OS (in months) is defined as:

- $[(\text{date of death or last known alive} - \text{date of first ELI-002 dose}) + 1]/30.4375$

#### **13.3.4. Safety Analysis**

Summary statistics (counts, percentage, mean, standard deviation, etc.) will be provided for the safety endpoints as appropriate.

Treatment-emergent adverse events (TEAEs) will be listed and tabulated by system organ class, preferred term, maximum CTCAE grade, relationship to trial treatment, outcome, and action taken with trial treatment. TEAEs will be tabulated by treatment regimen and overall and reviewed for potential significance and clinical importance. Adverse events qualifying as serious will be separately listed, along with any dose interruptions and reductions.

Significant PE findings and vital signs will be listed and summarized by treatment regimen. Clinical laboratory results will be presented in a listing including change from baseline and selected parameters will be summarized in shift tables. ECG derived data will be explored graphically and by summary statistics.

#### **13.3.5. Pharmacokinetics**

No pharmacokinetics analyses will be performed.

#### **13.3.6. Pharmacodynamics**

The pharmacodynamic response to ELI-002 will be assessed by evaluation of immunogenic responses to the vaccine.

## **14. DATA INTEGRITY AND QUALITY ASSURANCE**

### **14.1. Data Management and Case Report Forms**

Elicio and/or its designee will be responsible for the processing and quality control of the data. Data management will be performed as described in the sponsor's and/or designee's standard operating procedures (SOPs) for clinical studies and the study Data Management Plan. Adverse events will be coded using MedDRA and medications will be coded using the World Health Organization Drug Dictionary (WHO Drug).

The handling of data, including data quality control, will comply with regulatory guidelines (ie, current ICH E6) and the sponsor and/or designee SOPs.

The eCRF will be provided by the sponsor or its designee and should be completed in accordance with applicable study guidelines and within the timeframe specified. Each eCRF should be filled out completely by the investigator or designee as stated on the Delegation of Authority Log. All data entry in the eCRF must have corresponding source documentation located in the subject study records.

All data will be stored in a validated database that is 21 CFR Part 11 compliant. The principal investigator is responsible for ensuring the timely completion of eCRFs. The principal investigator (or sub-investigator) must review, sign and date the eCRFs at the time of study completion to attest to the accuracy and completeness of the study data at the clinical site.

### **14.2. Source Documentation**

Source documents are defined as documentation of the observations and activities of a clinical study. Source documents may include, but are not limited to, study progress notes, email correspondence, subject QLQs (or PROs), subject diaries, laboratory data and pathology and/or imaging reports. All source documents for this study will be maintained by the investigator and made available to the sponsor, the sponsor designee and regulatory authorities. The signed informed consent document and statement of consent will be maintained in the subject study records, and a copy of the informed consent will be provided to the subject.

### **14.3. Study Drug Accountability**

At all times, a record of the study drug inventory and study drug accountability must be maintained. Inventory and accountability records must be readily available to the study monitor, the sponsor, and any regulatory authority. The investigator, in conjunction with the site pharmacy or study drug preparation lab, is responsible for ensuring accountability of all used and unused study drug.

At the end of the trial, and following study monitor verification of drug accountability, Elicio or its designee will provide instruction for the destruction of unused study drug supplies remaining at the clinical site. During the conduct of the study, used vials may be destroyed on-site if Elicio has approved the destruction policy and only after the study monitor has verified drug accountability. If study drug destruction by the clinical site is approved by Elicio or its designee, the investigator must ensure that all study drug is destroyed in compliance with institutional

policy, applicable local regulations, as well as 21 CFR 312.59 and current ICH E6 guidelines pertaining to drug destruction. All destruction at the clinical site must be adequately documented.

#### **14.4. Laboratory Assessments**

Local laboratories will be responsible to analyze safety laboratory tests for this study. All local laboratory results will be captured on eCRFs. Central labs will be used for the analysis of pharmacodynamic and immunology assays, as well as specialty biomarkers.

#### **14.5. Trial Monitoring**

During the trial, Elicio and/or its designee will perform periodic monitoring visits to ensure that the protocol and ICH/GCP are being followed in the conduct of the study. Study monitoring will be performed in accordance with ICH/GCP, the sponsor and/or its designee's SOPs, the study protocol and study plans, as well as applicable local regulations. The monitor will maintain current personal knowledge of the study through observation, review of study records and source documentation, as well as discussion on the conduct of the study with the investigator and site staff. The monitor will review all study source documents to ensure that the eCRFs are completed and accurate.

The monitor, Elicio representatives and regulatory authorities will be given direct access to all study related documentation (such as medical charts/records, laboratory reports, diagnostic reports, study drug logs), study staff training documentation and institutional SOPs to verify study conduct. His verification may continue following completion of the study. It is important that the investigator and study staff are available during the monitoring visit and that sufficient time is devoted to items requiring follow-up or resolution.

#### **14.6. Protocol Deviations**

A deviation from the protocol is a departure from the procedures and/or processes approved by the sponsor and the IRB and agreed to by the principal investigator.

Protocol deviations will be reported to the sponsor or its designee as they occur or are discovered and must be documented as appropriate in the study source record. In addition, protocol deviations will be reported to the IRB per the individual IRB guidelines. The monitor will document deviations discovered throughout the course of monitoring visits and review of the eCRFs. These deviations, and any necessary corrective actions, will be reviewed and discussed with the sponsor and the investigators as applicable.

#### **14.7. Audits and Inspections**

During and/or after the completion of the study, authorized representatives of Elicio, a regulatory authority, or an IRB may visit the trial center to perform audits or inspections, including source data verification. The purpose of an audit or inspection, which is independent from routine monitoring, is to systematically and independently evaluate all trial-related activities and documents to determine whether these activities were conducted, according to the protocol, GCP and current ICH guidelines, and applicable regulatory requirements.

The investigators accept that by endorsing the protocol signature page that the sponsor, IRB or regulatory authorities may conduct an inspection to verify compliance to the protocol and GCP/ICH guidelines. Representatives of the sponsor, IRB or regulatory authority will be permitted direct access to source documents. It is important that the investigator and study staff are available during the inspection or audit and that sufficient time is given to addressing any questions or items that require resolution.

If a regulatory authority or IRB notifies the clinical site of an inspection related to the study, the investigator will immediately notify the sponsor. The investigator agrees to cooperate with Elicio or its designees, when possible, to be present at the inspection. The investigator also agrees to promptly provide the sponsor with copies of inspection findings. Before submitting a response to regulatory authorities, the investigator will give Elicio and/or its designees the opportunity to review the response and provide feedback.

